Despite evidence that both rapid weight gain⁷ and excessive body fat accrual⁸ are associated with overweight and obesity, usual neonatal care for preterm infants does not include the assessment of body fat accrual. Similarly, screening programs to assess body composition in infants with a history of prematurity have not been established. By monitoring body fat accrual in preterm infants before and after hospital discharge, clinicians could modify dietary interventions in early infancy and prevent obesity and long-term related morbidities. In this pilot randomized trial, we will test the central hypothesis that very preterm infants (28 to 32 weeks of gestation as defined by the World Health Organization) managed using information from monthly serial assessments of infant body composition from birth to hospital discharge will have lower percent body fat (%BF) at 3 months of age than infants managed using standard care (weight and other routine growth parameters). %BF at 3 months of age has a strong correlation with %BF at 4 years of age⁹. Our long-term goal is to develop a comprehensive nutritional program that incorporates assessment of body composition in the routine care of preterm infants and reduces variability in feeding practices before and after hospital discharge to minimize the risk of obesity mediated by rapid weight gain.

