Specific Aim 1: To test the hypothesis that provision of serial body fat accrual reports during hospitalization will enable personalized dietary interventions and reduce adiposity at 3 months of age in very preterm infants. We chose %BF at 3 months of age as the primary outcome of the trial because at this age: 1) body fat accrual can be measured with non-invasive methods¹⁰; 2) loss to follow-up rates are low⁹; 3) physical activity and other risk factors for obesity are less likely⁷; and 4) correlation with body fat accrual at preschool age is strong⁹. We selected very preterm infants as the ideal population to study the risk of obesity in preterm infants because they: 1) experience a high risk for adverse health outcomes^{3,5}; 2) usually do not require supplemental oxygen after postnatal day 7; and 3) receive strictly controlled diets for more than 30 days from birth to hospital discharge. With our improved understanding of the interaction between infant weight, body fat accrual, and dietary interventions, we plan to examine whether the provision of body fat accrual reports to clinicians and parents will impact infant weight gain and body fat accrual¹¹.

Specific Aim 2: To test the hypothesis that serial assessment of infant body composition attenuates health disparities in body fat accrual at 3 months of age by slowing weight gain following hospital discharge. The rationale for this aim is: 1) rapid weight gain during early infancy is highly prevalent among racial/ethnic minorities^{12,13}; and 2) adjustment for rapid weight gain attenuates disparities in childhood obesity between racial/ethnic minorities and white infants^{7,12}. We hypothesize that our intervention focused on personalized dietary interventions based on changes in infant body composition will reduce rapid weight gain and attenuate health disparities in body fat accrual.

RESEARCH STRATEGY

SIGNIFICANCE

Rapid weight gain increases the risk of metabolic reprogramming in preterm infants. For many years, the high prevalence of postnatal growth failure (weight below the 10th percentile for expected intrauterine growth) in the preterm population made weight the most important outcome of growth among preterm infants. Similarly, the association between rapid weight gain and improved neurodevelopment led clinicians to assume that slow weight gain was “inadequate growth” and that high-calorie diets to promote rapid weight gain were needed.

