Slow weight gain after hospital discharge attenuates the risk of obesity among racial/ethnic minorities. Observational studies show that obesity and rapid weight gain in early infancy are more prevalent among blacks and Hispanics than among whites and that differences in feeding practices (breastfeeding rates, early introduction of complimentary foods and others) contribute to these disparities in infant weight gain and obesity^{12,13}. Adjustment for these early risk factors related to infant feeding attenuates disparities in childhood obesity between minority and white infants^{7,12}; therefore, it is plausible that, by providing more specific information about early changes in body composition instead of using an anthropometric index, clinicians and parents may alter their feeding regimens before and after hospital discharge in a manner that will reduce the risk for unhealthy gains in adiposity. Modifications of these early risk factors could have a substantial impact on preventing disparities in childhood obesity¹².

INNOVATION

Despite clinicians' ability to effectively control all external sources of nutrition in the immediate neonatal period, current dietary interventions and methods to assess postnatal growth have not led to significant improvement in growth and neurodevelopment. Comprehensive evaluation of postnatal growth with infant body composition is essential to guide appropriate and effective nutritional interventions for infants at high risk of obesity.

The incorporation of a longitudinal assessment of infant body composition into current practices of neonatal care is innovative because it will provide a more sensitive index of the infant's body habitus and thereby guide clinician decisions about dietary interventions. This change in practice could reduce the risk of overweight and obesity in very preterm infants.

Serial assessment of infant body composition using air-displacement plethysmography, a validated method with reliable accuracy, to report body fat accrual in a randomized clinical trial is also one of the novel aspects of our proposal, as other research studies have used low-accuracy methods to estimate infant body composition⁶.

APPROACH

Our central hypothesis is that very preterm infants managed using information from serial assessments of infant body composition during their initial hospitalization will have lower percent body fat (%BF) at 3 months of age, irrespective of sex and race/ethnicity.

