Specific Aim 1 will test the hypothesis that, after establishing a program to monitor infant body composition before and after hospital discharge, identification of changes in body fat accrual will prompt individualized recommendations for dietary interventions that reduce %BF at 3 months of age in very preterm infants.

Overview: Aim 1 will be a pilot randomized trial in which 50 very preterm infants will be randomly assigned in a 1:1 allocation ratio to either routine neonatal care (control group) or neonatal care with serial assessments of infant body composition (intervention group). The primary outcome will be %BF at 3 months of age [Table 1].

Table 1. Project timeline

Critical steps	Month											
	Jun	Jul	Aug	Sep	Oct	Nov	Dec	Jan	Feb	Mar	Apr	May
Anticipated IRB approval (protocol & consent form)												
Patient screening and enrollment												
Body fat assessment at 3 months of age												
Primary & secondary data analyses												
Results available for manuscript preparation												

Rationale: While weight, the key element of the operational definition of postnatal growth failure, remains useful to assess nutritional status, its limitations as the only method to assess nutritional status and health risks⁴¹ should not be ignored. The assumed benefit of catch-up growth on neurodevelopment should be weighed against the possibility that catch-up growth might cause harm and increase the risk of adult-onset metabolic disease^{24,26,42}. Because infant weight gain predicts later obesity risk⁴³, central adiposity⁴⁴ and insulin resistance⁴⁵, more research is needed to define the best strategies to provide adequate nutrition with a goal of preventing growth failure without increasing health risks of public health importance. The problem of increased adiposity soon after birth and into adulthood among preterm infants suggests that assessment of body fat accrual along with weight gain could be an effective strategy to achieve the goal of ideal growth while preventing unnecessary health risk. As defining the risk for abnormal cardiovascular and metabolic outcomes in this population has become critically important⁴⁶, it is possible that early detection of atypical changes in infant body composition characterized by excessive body fat accrual could prompt changes in dietary interventions to reduce the risk of obesity, cardiovascular disease, and metabolic syndrome later in life.

Study design

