Setting: The neonatal unit at UAB is one of the largest neonatal academic centers in the United States. We have admitted more than 200 very preterm infants over the past 2 years. This large numbers of very preterm infants admitted makes our unit the ideal environment to conduct comparative effectiveness trials.

Participants: Very preterm infants with gestational ages between 28 and 32 weeks of gestation at the time of admission to our neonatal unit will be eligible for this trial. Gastrointestinal or neurologic malformations, and terminal illness requiring limited or withheld support will be exclusion criteria.

[figure not shown]
Randomization, allocation concealment, and masking: After receiving approval by the Institutional Review Board (IRB) at UAB to conduct this trial, research nurses and investigators will obtain written parental consent before randomization. We will randomize study participants using computer generated random-block sequences and numbered, opaque, sealed envelopes that will be opened in sequential order. Twin infants will be randomized individually. The intervention will not be masked.

Intervention: Infants randomly assigned to the intervention group will have the information about infant body composition known to the clinicians caring for them (including reference data). The use of this patient-specific information about nutritional status will assist clinicians to optimize nutrition using feeding guidelines that will be provided. Infants randomly assigned to the control group will also undergo serial measurements of body composition, but this information will not be available to the clinicians.

Primary and secondary outcomes: The primary outcome will be %BF estimated by air displacement plethysmography at 3 months of age. Secondary outcomes will include %BF and fat-free mass (FFM) at 36 weeks of postmenstrual age (PMA) or hospital discharge (whichever occurs first), postnatal growth restriction (below 10th percentile) at 36 weeks PMA or discharge, weight gain (g/kg/d) from birth to the end of the intervention, anthropometric measures at time of hospital discharge (weight, head circumference, and length), weight gain (g/kg/d) from hospital discharge to 3 months of age, anthropometric measures at 3 months of age (weight, head circumference, and length), and blood pressure values at 3 months of age.

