Assessment of infant body composition: Serial assessments of infant body composition with air displacement plethysmography in very preterm infants using the PeaPod® (Life Measurement Instruments, Concord, CA)³² will occur in the first 14 days after birth (baseline measure), at 32 weeks PMA, at 36 weeks PMA or hospital discharge (whichever occurs first), and at 3 months of age [Figure 2]. The PeaPod® and the neonatal unit are located in the same building. During hospitalization, nursery staff and parents, if present, will transport the infant to the exam room where the PeaPod® is located. In the exam room, nursery staff will undress the infant, place the snug cap, and transfer the infant to the PeaPod® when ready for weighing and scanning. The infant will wear only a cap on his/her head and will lie inside the scanner for approximately 2-3 minutes to estimate total fat and fat-free mass according to body weight and volume⁴⁷. The infant will breathe the normal air in the room and will be able to see and hear his/her parents. Equipment for respiratory support or monitoring will not be used during the assessment to avoid unnecessary recalibration of the PeaPod®. For assessment of body composition at 3 months of age, a follow-up visit will be scheduled prior to discharge from the hospital. The 3-month visit will also include a brief questionnaire about feeding practices at home and blood pressure measurements. The study coordinator will mail a reminder letter approximately 2 weeks prior to the date of the visit and will call the caregiver to remind them on the day prior to their scheduled appointment. Infants and a caregiver will return to the hospital to repeat the body composition assessment. A trained technician from the Nutrition Obesity Research Center (which owns and manages the PeaPod®) will operate it.

Figure 2. Serial assessment of body fat accrual in very preterm infants*

* Traditional growth chart report (A) and body fat accrual report (B) of a preterm infant born at 29 weeks of gestation and monitored from birth to 36 weeks PMA

Control or monitoring of co-interventions: Clinical care and decisions about enteral nutrition will be conducted at the discretion of the attending physician.

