Protections against Risk. Our team will make every effort to protect all participants' confidential and private information in order to minimize possible study-associated risks. All findings related to any research will be available and provided to study participants in accordance with standard practices. We will also inform all participants that their participation is voluntary, and we will utilize study identification codes in place of personal identifiers on study materials. We will also employ storage and encryption techniques in compliance with UAB Data Security standards to safeguard all electronic data, as well as protections outlined in Subpart C of title 45, part 4 Code of Federal Regulations. All study personnel are required to renew Human Subjects training biannually. No data will be accepted from or distributed to the principal investigator or study staff if regulatory training is not current.

Any provider or caregiver involved in the trial will be able to write to the study coordinator to draw attention to any concern they may have about the possibility of harm arising from the intervention under investigation.

Potential Benefits of the Proposed Research to Human Subjects and Others

Potential benefits of this study are to provide stronger evidence for the safety and efficacy of monitoring body fat accrual as a way of optimizing caloric intake, growth, and fat-free mass in preterm infants. Better quantitative and qualitative outcomes of growth may also be associated with improved long-term neurodevelopmental outcomes.

The potential benefits of this research may include reduction of postnatal growth restriction, reduction in infant morbidity mediated through improved neonatal nutrition, and better growth at time of discharge. Reductions of postnatal growth restriction and improved nutritional parameters could improve long-term neurodevelopmental outcomes of infants. There will be benefit to the medical community in providing additional information on infant body composition in preterm infants.

Importance of the Knowledge to be Gained

As the risk to individual participants is small and potential benefits are significant, the risk/benefit ratio is favorable.

ClinicalTrials.gov Requirements

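### Control infants' body-composition results are withheld from clinicians only, so the visible text leaves open a route by which control parents could learn them before the 3-month outcome

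*Combined protocol and SAP*

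**What the plan says.** All places are in the combined protocol and SAP.

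- **Study design, Intervention.** Clinicians caring for intervention infants receive the body-composition results, with reference data and feeding guidelines. Control infants are measured too, "but this information will not be available to the clinicians". Parents are not mentioned in either arm. The preceding paragraph states that the intervention is not masked.
- **Specific Aim 1 (opening statement of aims).** The investigators plan to examine whether "the provision of body fat accrual reports to clinicians and parents will impact infant weight gain" and body fat accrual.
- **Significance.** It is called plausible that, given this information, "clinicians and parents may alter their feeding regimens before and after hospital discharge".
- **Assessment of infant body composition.** For hospital scans, "nursery staff and parents, if present, will transport the infant to the exam room", with no distinction by arm. Later in the same section: "The 3-month visit will also include a brief questionnaire about feeding practices at home".
- **Protections against Risk.** "All findings related to any research will be available and provided to study participants in accordance with standard practices".

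The comparator is described as "standard care (weight and other routine growth parameters" in the central hypothesis. The Aim 1 overview describes the arms as "either routine neonatal care (control group) or neonatal care with serial assessments of infant body composition (intervention group"). The primary outcome is %BF at 3 months of age.

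**The concern.** The randomized contrast is access to the body-composition information. Control infants generate the same information, so the contrast depends on who is kept from seeing it. The only withholding rule names clinicians, which reasonably includes bedside nurses. Parents are left out, although the aims and background describe them as people who might receive the reports and change feeding because of them.

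Parents do the feeding between discharge and the primary measurement. A control family that learned its infant's %BF early would hold part of the tested strategy. The arms would then most likely move closer together on the primary outcome. This cannot be undone at analysis. The 3-month questionnaire is described as covering feeding at home, with no mention of whether the family knew the result, so a null finding could not be separated from contamination.

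**Working it through.** **1. Reading the passages together.** A coordinator is asked by a control parent for the discharge %BF.

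- The Intervention paragraph forbids telling clinicians and is silent on parents.
- The Protections against Risk sentence, read literally, favours release to participants, with no exception for controls and no timing. Its qualifier about standard practices does not settle the matter.
- The assessment section lets parents be at the hospital scan, so the question is foreseeable. Nothing there says a value is shown or spoken.

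Early release is therefore permitted by the visible text, but not described by it.

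**2. The plan's own sample size.** Inputs from Sample Size and Power Estimates: difference 3 points, SD 3.6, alpha 0.05 (taken as two-sided), power 80%.

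- Normal approximation: n per arm = 2 × [(1.960 + 0.842) × 3.6/3]² = 22.6, rounded up to 23, so 46 in total. This reproduces the stated 46.
- The exact t calculation gives 23.6, so 24 per arm and 48 in total.
- With 50 randomized and 10% lost, 45 are evaluable, an average of 22.5 per arm. Exact two-sided t power is then 78.0%.

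**3. Bound per disclosed infant.** Assume disclosure gives a control infant no more than the full 3-point effect. Among 22.5 evaluable controls, one such infant moves the control mean by at most 3/22.5 = 0.13 point. Dividing by all 25 randomized controls would give 0.12, but the evaluable number is the right basis for the analysed contrast.

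**4. Illustrative range.** The documents give no disclosure rate and no effect of disclosure, so both are assumptions. Contrast = 3 × (1 − share disclosed × fraction of full effect). Power is exact two-sided t, SD 3.6, 22.5 per arm.

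| Share of controls disclosed | Fraction of full effect | Contrast (points) | Power |
|---|---|---|---|
| 0% | – | 3.00 | 78.0% |
| 10% | 0.25 | 2.925 | 75.9% |
| 10% | 0.5 | 2.85 | 73.8% |
| 20% | 0.5 | 2.70 | 69.1% |
| 30% | 0.5 | 2.55 | 64.2% |
| 30% | 1.0 | 2.10 | 48.1% |

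The last row is an implausible extreme, because control parents would have neither the reference data nor the clinician-led changes in hospital.

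**5. Time at home before the outcome.** Assume discharge at 36 weeks postmenstrual age, 3 months = 13 weeks and term = 40 weeks.

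- Chronological age: 13 − (36 − 28) = 5 weeks to 13 − (36 − 32) = 9 weeks, out of 13 (38% to 69%).
- Corrected age, if that is meant: 53 − 36 = 17 weeks, out of 53 − 32 = 21 to 53 − 28 = 25 (81% to 68%).

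This shows how long parents control feeding. It says nothing about how often disclosure would occur or what it would do.

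**The case against.** The strongest reply is that the gap is unconfirmed. What parents are told about their infant's results belongs naturally in the consent form, which is not in the review copy, and the figure in the design section is not shown either. Either might restrict disclosure. This stands, and it is the main reason the point is minor.

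The parental role can also be read narrowly. The operative text defines the intervention through clinicians, and the central hypothesis concerns management in hospital. The Significance passage says only that parental action is plausible, and the sentence in Specific Aim 1 may describe a later step. This stands in part: the documents do not establish that even intervention parents receive reports. But the sentence sits inside Specific Aim 1, so a parental role cannot be set aside.

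The return-of-findings sentence sits among confidentiality provisions and may mean overall study findings, not an infant's interim scan values. That reading is reasonable. The wording does not exclude the literal one, and staff have nothing else visible to follow.

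Finally, all the dilution figures are assumed, the milder cases cost only about 2 to 4 percentage points of power, and the bias runs toward no difference, so it would not create a false benefit. All of this stands.

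A reader might go further and infer that control parents will be given the results, or that attending the scan discloses them. The documents support neither: the first rests on silence plus a general sentence, and the second on presence alone.

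**Conclusion.** The point holds as an open route. The visible text withholds control results from clinicians, not from parents, and its one general rule on findings has no control-arm exception or delay. It does not show that disclosure will occur.

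The likely direction is dilution toward no difference. The size is unknown. The only firm statement is the bound of about 0.13 point of the 3-point contrast per disclosed evaluable control infant, on the assumption that disclosure carries no more than the strategy's full effect. A reader might take the lower rows of the table as expected losses of power; they are not, because no disclosure rate or effect can be drawn from the documents.

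Severity is minor. It is still worth acting on, because contamination could not be corrected or even detected afterwards, and exact-t power is already slightly below 80%. If the consent form already prevents early release, the remaining task is to make the protocol text agree with it.

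**What to change.** 1. In the Intervention paragraph, state that control results go to the research file only and are not given to clinicians or parents until after the 3-month %BF measurement, except for a logged safety reason.
2. In Protections against Risk and in the consent form, limit release of a control infant's own results to after that visit.
3. Record any earlier disclosure per infant, in one field.

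**Cost.** This is a cheap improvement: a few sentences, one instruction to the scan technician and one data field. Sample size, comparator, feeding guidance and analysis do not change. The consent wording may need IRB review. The ClinicalTrials.gov Requirements section places IRB submission after peer review of the protocol, so a change made before then goes into the first submission.

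**Downside and limit.** Control parents wait until the 3-month visit for their infant's result. Twins are randomized individually, so a family with twins in different arms could still learn the intervention twin's result if parents receive reports. The log should flag those pairs.

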Air-displacement plethysmography (PeaPod®, Life Measurement Instruments, Concord, CA) is one the less invasive and more accurate methods to assess infant body composition in early infancy^{32,34}. Using air-displacement plethysmography, several studies have determined reference values of neonatal body fat accrual at different gestational ages^{6,10}. At birth, body fat accrual expressed as %BF ranges from 6% at 30 weeks of gestation to 9.5% at 37 weeks of gestation.¹⁰ At term-equivalent age, all preterm infants have significantly higher %BF than infants born at term (up to 6% higher when measured by air-displacement plethysmography)²⁹, irrespective of history of intrauterine growth restriction³⁵.

While studies that assessed infant body composition with either dual energy X-ray absorptiometry or bioelectrical impedance analysis suggest that fat free mass (FFM) can be predicted using weight data³⁶, studies that assessed infant body composition with air-displacement plethysmography, a method with high accuracy and validity when compared to the gold standard carcass analysis³², suggest an unreliable correlation between anthropometric data and neonatal adiposity³⁷ and body composition³⁰ in preterm infants.

Body fat accrual at 3 months of age predicts infant body composition at 4 years of age. Unlike body composition at term-equivalent age, body composition at 3 months of age has a strong correlation with body composition at 4 years of age in infants born preterm⁹. Large observational studies suggest that differences in body composition between term and preterm infants persist into adulthood^{4,5}, but the implications of early alterations of growth and body composition are largely unknown despite evidence that early rapid weight gain and body fat accrual are determinants of later obesity risk in full-term and preterm infants^{5,38-40}. Taken together, these data suggest that early changes in body composition following hospital discharge could be an important outcome of growth to analyze long-term health risks of rapid weight gain and body fat accrual during early development. Serial monitoring of body composition during infancy may allow nutritional support optimization that balances neurodevelopmental benefit and metabolic risk⁹.

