Study specimens. Because several experiments suggest that changes in gut microbiota can influence obesity⁴⁸, we will obtain written informed consent from the parent(s) to collect 2 stool samples, 1 stool sample before hospital discharge and 1 stool sample at the 3-month follow-up visit for possible use in future studies. Similarly, consent from the parent(s) will be obtained to collect a serum sample and measure biomarkers of anabolism and growth prior to hospital discharge.

Statistical Analysis Plan. This trial will record core data on nutrition as recommended by consensus groups⁴⁹. For analysis of the primary outcome, an unadjusted T-test comparison of the mean %BF between control and intervention groups will be performed assuming a normal distribution of this variable⁵⁰. In consideration of relevant biological variables, a pre-specified adjusted analysis for demographic and nutritional characteristics will be conducted to improve precision in treatment comparisons and remove variability associated with these covariates^{51,52}. A similar approach will be used for secondary outcomes. Descriptive data will be expressed as the mean (SD) or number (percentage) of observations. The primary statistical analyses will be performed on an intention-to-treat basis⁴⁹ with SAS software.

Sample Size and Power Estimates. At our institution, the mean and SD of %BF in preterm infants at time of discharge is 15 and 3.6, respectively (unpublished data). Therefore, to detect a 3-point difference in %BF between groups with SD of 3.6, 0.05 level of significance, and 80% power for a T-test that compares means from two independent samples, a sample size of 46 patients will be necessary in this superiority trial. Anticipating that approximately 10% of study participants will be lost to follow-up for assessment of the primary outcome at 3 months of age, 2 patients will be added to each group and the sample size will be increased to 50. We will include a total of 25 patients in each group (n=50).

Potential Problems

Enrollment rates: An average of 7 study participants per month were enrolled in a recently completed trial that assessed body composition of very preterm infants at our institution (unpublished data). To define a timeline for patient enrollment in this trial, we assumed that 50% of parents will refuse participation.

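### Secondary outcomes measured at discharge, or at 36 weeks PMA if earlier, are compared as raw means although age at measurement may differ between arms

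*Combined protocol and SAP*

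**What the plan says.** Two timing rules apply, both in the protocol's list of primary and secondary outcomes.

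- **Body composition.** Percent "BF and fat-free mass (FFM) at 36 weeks of postmenstrual age (PMA) or hospital discharge (whichever occurs first"). The section on assessment of infant body composition repeats the rule for the scan schedule: "at 36 weeks PMA or hospital discharge (whichever occurs first), and at 3 months of age". It gives no window for the scan.
- **Size at discharge.** "anthropometric measures at time of hospital discharge (weight, head circumference, and length"). No age limit is attached.

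On analysis, the Statistical Analysis Plan specifies for the primary outcome an unadjusted t-test on mean %BF, plus a pre-specified adjusted analysis with demographic and nutritional covariates. It then adds: "A similar approach will be used for secondary outcomes". PMA at measurement is not named as a covariate, and no z-score is listed as an outcome.

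On conduct, "The intervention will not be masked". The body composition information "will assist clinicians to optimize nutrition using feeding guidelines that will be provided", and "Clinical care and decisions about enteral nutrition will be conducted at the discretion of the attending physician". No discharge criteria are given.

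**The concern.** Weight, length, head circumference, FFM and %BF all increase with age over this period. When discharge sets the time of measurement, a raw mean reflects both the infant's growth and the age at which it was measured. Randomisation balances what precedes it, but discharge comes afterwards. It is in the hands of clinicians who know the allocation, and it plausibly depends on feeding and weight gain, which the intervention is meant to change.

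If slower weight gain delayed discharge, intervention infants would be measured older and would look larger or fatter, hiding an effect. If stays were shortened, the distortion would reverse. These outcomes are the direct read-out at the end of the in-hospital intervention, so a difference in stay could be mistaken for a difference in growth or adiposity.

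The two rules differ in exposure. Discharge anthropometry has no cap, so every infant contributes. For %BF and FFM the scan is fixed at 36 weeks PMA for any infant still in hospital, so only earlier discharges contribute.

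**Working it through.** **1. The plan's own figure.** Sample Size and Power Estimates uses a 3-point difference, SD 3.6, 0.05 significance (taken as two-sided) and 80% power. By the normal approximation, n per arm = 2 × (1.960 + 0.842)² × 3.6² / 3² = 22.6, rounded up to 23, so 46 in total. This reproduces. It concerns %BF at 3 months. The documents give no target or power for the outcomes discussed here, so the 3-point difference is not a yardstick for them.

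**2. Change of %BF with age.** The Significance section states: "At birth, body fat accrual expressed as %BF ranges from 6% at 30 weeks of gestation to 9.5% at 37 weeks of gestation". Slope = (9.5 − 6) / (37 − 30) = 0.5 points per week. This is the only slope that follows directly from the documents, and it compares different infants at birth.

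A steeper in-hospital slope is an assumption. The site's mean %BF at discharge is 15. Starting from 6% at 30 weeks and placing discharge at 36 weeks, (15 − 6) / (36 − 30) = 1.5 points per week.

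**3. Shift in %BF.** Shift = slope × difference in arm-mean PMA at scan. The difference is assumed to be 0.5 week.

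- 0.5 × 0.5 = 0.25 points
- 1.5 × 0.5 = 0.75 points

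The standard error of the comparison with 25 per arm and SD 3.6 is 3.6 × √(2/25) = 1.02 points. With no true effect, a two-sided 5% t-test would reject 5.7% of the time at a 0.25-point shift and about 11% at 0.75.

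**4. Effect of the 36-week cap.** Difference in arm-mean PMA = share of infants affected × mean shift among them. If 25% are affected (assumed), a 0.5-week difference in arm means needs 0.5 / 0.25 = 2 weeks in each of them. If instead that 25% shift by 0.5 week:

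- 0.5 × 0.25 × 0.5 = 0.06 points, rejection 5.0%
- 1.5 × 0.25 × 0.5 = 0.19 points, rejection 5.4%

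The documents do not give the share leaving before 36 weeks. Specific Aim 1 describes controlled diets for more than 30 days before discharge. Since 30 / 7 = 4.3 weeks, an infant born at 32 weeks would reach 32 + 4.3 = 36.3 weeks, but one born at 31 weeks reaches only 35.3 and one born at 28 weeks only 32.3. Discharge before 36 weeks is therefore not ruled out.

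**5. How much a reference chart corrects.** An at-birth reference rising 0.5 per week removes 0.5 / (actual slope) of the timing effect. If infants gain 1.0 points per week, from (15 − 8) / 7, the share removed is 50%. If they gain 1.8, from (15 − 6) / 5, it is 28%. The 8% start and the 5- and 7-week intervals are assumptions. At 1.5 per week and a half-week difference, 0.75 − 0.25 = 0.50 points would remain.

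**6. Not quantified.** The documents give no weekly change for FFM, length or head circumference, and none usable for discharge weight, so no figure is offered for these.

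**The case against.** The case against has real force. The cap fixes the scan for everyone still in hospital at 36 weeks, and a delayed discharge can never push the scan beyond that age. With a modest share of early leavers the shift is too small to matter, and even 0.75 points is less than one standard error. The steeper slope depends on where the site's discharge value is placed in time, and that value is for preterm infants in general. No passage says that the intervention moves discharge. The adjusted analysis extends to secondary outcomes. Postnatal growth restriction is already judged by percentile, and weight gain in g/kg/d is a rate, so neither is exposed in the same way.

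All of this stands as a limit on size. It does not remove the point. Demographic and nutritional covariates do not include age at the scan, and gestational age at birth would not substitute for it. The cap does nothing for discharge weight, length and head circumference.

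A reader might infer that all end-of-hospital comparisons are biased, or take the extreme in which every infant in one arm is scanned a week earlier at 1.5 points per week. That would give a 1.5-point shift and about 30% false rejection. It would require discharge before 36 weeks throughout that arm, which the documents do not support.

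**Conclusion.** The point holds for secondary outcomes only. Discharge anthropometry is exposed in all infants, and %BF and FFM only in those discharged before 36 weeks. For %BF, an assumed half-week difference in arm-mean PMA at scan gives about 0.25 points at the documented slope and about 0.75 at an assumed 1.5 points per week. The shift is close to zero if few infants leave early or if timing is the same in both arms. That discharge timing can respond to the intervention is an inference from the design, not a statement in the documents.

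A reader might also infer that the trial's main result is in doubt. It is not on this ground: %BF at 3 months and the planned 50 infants are unaffected. The change is worth making because the plan as written would neither reveal nor handle a difference in timing.

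**What to change.** 1. Record PMA at each scan and at discharge, and report both by arm.
2. Make PMA- and sex-specific z-scores, from a chart named in advance, the main analysis of discharge weight, length and head circumference. Keep raw means as description.
3. For %BF and FFM at 36 weeks or discharge, report PMA-standardised values beside the raw means. Add a sensitivity analysis that models the existing serial scans on actual PMA and compares the arms at a common age. Simply adding PMA at scan to the adjusted model is less clean, because it is itself measured after randomisation.

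The cost is a few sentences in the SAP and some calculation. PMA follows from the dates and gestational age at birth, and no extra visit or scan is needed. The downside is that results depend on the chosen chart. At-birth %BF references correct only part of the timing effect (about 28% to 50% if infants gain 1.0 to 1.8 points per week), so the raw means and the longitudinal model should be shown as well.
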